9. SAFETY REPORTING

Adverse events and device deficiencies, noted by study staff and reported by the subject, and occurring from the time of study device implantation through study completion should be recorded on the appropriate CRFs and reported as below.

9.1. Definitions for safety reporting

A. Adverse Event (AE)

An AE is any untoward medical occurrence, unintended disease or injury, or untoward clinical signs (including abnormal laboratory findings) in subjects, users or other persons, whether or not related to the investigational medical device [1].

This definition includes:

- events related to the investigational medical device or the comparator
- events related to the procedures involved

B. Serious Adverse Event (SAE)

A SAE is an adverse event that [1]:

- led to death,
- led to serious deterioration in the health of the subject, that either resulted in:
 - 1) a life-threatening illness or injury, or
 - 2) a permanent impairment of a body structure or a body function, or
 - 3) in-patient or prolonged hospitalization, or
 - 4) medical or surgical intervention to prevent life-threatening illness or injury or permanent impairment to a body structure or a body function
- led to fetal distress, fetal death or a congenital abnormality or birth defect

Planned hospitalization for a pre-existing condition, or a procedure required by the protocol, without serious deterioration in health, is not considered a serious adverse event.

C. Adverse Device Effect (ADE)

An ADE is an adverse event related to the use of an investigational medical device [1].

This definition includes:

- adverse events resulting from insufficient or inadequate instructions for use, deployment, implantation, installation, or operation, or any malfunction of the investigational medical device.
- any event resulting from use error or from intentional misuse of the investigational medical device.

D. Serious Adverse Device Effect (SADE)

An SADE is an adverse device effect that has resulted in any of the consequences characteristic of a serious adverse event [1].

E. Unanticipated Serious Adverse Device Effect (USADE)

A serious adverse device effect which by its nature, incidence, severity or outcome has not been identified in the current version of the risk analysis report or the clinical investigation plan [1,2].

F. Device Deficiency

A device deficiency is an inadequacy of a medical device with respect to its identity, quality, durability, reliability, safety or performance. Device deficiencies include malfunctions, use errors, and inadequate labelling.

For the purpose of this study, device deficiencies should be reported when they concern any component of the study device or any components of the Journey II implants, as well as its packaging and tools that need to be used during implantation according to the Instructions for Use.

G. Revisions

A specially designed Revision Case Report Form will be used in addition to the Adverse Event Form, to document in detail revisions of any of the components of the study device.

9.2. Safety: Investigator's Responsibilities

Investigators shall record adverse events and observed device deficiencies, together with an assessment of seriousness, severity, and relatedness, in the subject's source data. Following, Investigators are responsible for documenting AEs and device deficiencies on the appropriate CRF and submitting them to the Sponsor according to the timelines described here below.

At each contact with the subject, the Investigator must seek information on AEs by specific questioning and, as appropriate, by assessment of the subject. AEs must be recorded in Standard English medical terminology.

Unresolved AEs should be followed by the Investigator until the events are resolved, the subject is lost to follow-up or through to the end of the study, whichever timing occurs first. Unresolved AEs at the end of the subject's participation will be monitored by the Investigator as part of the site's normal standard of care.

The Investigator will categorize AEs as mild, moderate or severe based on the following definitions:

- Mild: the subject is aware of the sign or symptom, but finds it easily tolerated. The event is of little concern to the subject and/or little clinical significance. The event is not expected to have any effect on the subject's overall health or wellbeing.
- Moderate: the subject has discomfort enough to cause interference with or change in usual activities. The event is of some concern to the subject's health or wellbeing and may require medical intervention and/or close follow-up.
- Severe: the adverse event interferes considerably with the subject's usual activities. The event is of definite concern to the subject and/or poses substantial risk to the subject's health or wellbeing. The event is likely to require medical intervention and/or close follow-up and may be incapacitating or life threatening. Hospitalization and treatment may be required.

The Investigator is responsible for describing the relationship of the AE to Navio (the study device), the implant and the procedure based on the following definitions:

- Unrelated: the event is clearly not related to the study device or procedure
- Possible: the event may or may not be related to the study device or procedure. A relationship cannot be ruled out.
- Definite: the event is clearly related to the study device or procedure.

9.3. Timelines for Submission of Safety Information:

The timelines begin when the Investigator becomes aware of the event.

The Investigator will report to the Sponsor:

- As soon as possible, but no greater than **24 hours upon becoming aware of the event, SAEs*, SADEs, U(S)ADEs and device deficiencies that could have led to a SADE:**
 - if suitable action had not been taken
 - if intervention had not been made, or
 - if circumstances had been less fortunate

- **Revisions, within 24 hours upon becoming aware of the event.** Sponsor will provide an explant retrieval kit on becoming aware of a revision and ask the Investigator to return any revised components for retrieval analysis.

Investigators may also be asked to supply the Sponsor, upon Sponsor's request, with any additional information related to the safety reporting of a particular event.

The Principal Investigator will be responsible for reporting to the IRB/EC of the study site and to the regulatory authorities, SAEs, SADEs and device deficiencies that could have led to a SADE, as required by the national regulations.

9.4. Safety reporting: Sponsor's Responsibilities

Sponsor will provide progress reports on safety events to the Investigator to report to the IRB/EC as required.

In the case of multicenter studies, Sponsor will inform all Investigators in writing of all SAEs that were reported by all sites throughout the clinical investigation and based on perceived risk.

The Sponsor will also, in case of SADEs and device deficiencies that could have led to SADEs, determine whether the risk analysis needs to be updated and assess whether corrective or preventive action is required.

10. STATISTICAL PROCEDURES

10.1. Sample size calculation

Parratte et al.⁷ looked at the effects of postoperative mechanical axis alignment on the survival of TKAs. They found that of the 398 TKAs reviewed in the paper there were 292 (73.4%) which post-operatively were defined as mechanically aligned (with a mechanical axis of $0^\circ \pm 3^\circ$).

This study aims to show superiority in the proportion of TKAs post-operatively defined as mechanically aligned against the reference proportion of 73.4% from above.

It is estimated that the proportion of mechanically aligned TKAs using the Navio system will be around 88%. If this assumption holds then the recruitment of 115 subjects would be sufficient to provide 80% power to show that the lower limit of the two-sided 95% confidence interval for the proportion of mechanically aligned TKAs is greater than 73.4%, hence proving superiority to the reference literature. It is expected that approximately 5% of subjects will be lost to follow up at the 1 month visit and therefore 120 subjects will be recruited for this study.

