11. ETHICAL CONSIDERATIONS	20
11.1. Ethical Approval	20
11.2. Protocol Amendments	20
11.3. Informed Consent	20
11.4. Risk – Benefit Analysis	20
A. Study Related Risks	20
B. Study Related Benefits	21
12. MONITORING PROCEDURES	21
12.1. Source Documentation	21
12.2. Direct Access	21
12.3. Site Qualification Visit	21
12.4. Site Initiation Visit	21
12.5. Interim Monitoring Visits	22
12.6. Closeout Visit	22
12.7. Sponsor Audits and Regulatory Inspection	22
12.8. Data Handling and Record Keeping Requirements	22

12.9. Data Recording and Record Retention	22
13. DEVIATIONS FROM PROTOCOL.....	23
13.1. Protocol Deviation Reporting Requirements	23
14. Publication policy.....	23
BIBLIOGRAPHY	24
Appendix 1	
JOURNEY II BCS and CR Component Part Numbers.....	28

ABBREVIATIONS & DEFINITIONS

AE	Adverse Event
ADE	Adverse Device Effect
AP	Anteroposterior
CAPA	Corrective and Preventive Action
CRO	Contract Research Organization
CRF	Case Report Form
EC	Ethics Committee
EQ-5D	EuroQuol 5D
FDA	Food and Drug Administration
FU	Follow-Up
GCP	Good Clinical Practice
ICF	Informed Consent Form
ICH	International Conference on Harmonisation of Technical Requirements for Registration of Pharmaceuticals for Human Use
IRB	Institutional Review Board
ITT	Intention to Treat Population
KSS	Knee Society Score
PI	Principal Investigator
PP	Per-protocol Population
QoL	Quality of life
SAE	Serious Adverse Event
SADE	Serious Adverse Device Effect
TKA	Total Knee Arthroplasty
USADE	Unanticipated Serious Adverse Device Effect

Protocol Synopsis:

Title of Study:	Clinical, Radiographic, and Patient-reported Outcomes associated with the use of the Navio [°] Robotic-assisted Surgical System in Total Knee Arthroplasty
Study Type:	Evidence Generation
Study Device:	Navio [°] Robotic-assisted Surgical System
Study Purpose:	To demonstrate superior accuracy with the Navio [°] Robotic-assisted Surgical System in achieving desired post-operative mechanical alignment, compared to TKA procedures using standard instruments, as well as to document clinical and patient-reported outcomes in subjects receiving TKA with the Navio [°] system.
Study Design:	Multicenter, prospective single-arm cohort study with historical control.
Primary Endpoint:	Post-operative Mechanical Alignment (percentage of subjects achieving target alignment, defined as $\pm 3^\circ$ from target) at one month post-operative.

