4. STUDY DESIGN

This is a multi-center, prospective cohort study with a comparison to historical control to collect 2-year safety and effectiveness data on 120 subjects, at approximately 6 sites in the United States, who have undergone Navio System-assisted TKA.

Subject data will be evaluated at the pre-operative, operative, one month, six months, one year, and two year follow up visits.

A final analysis will be conducted once all subjects have completed a two year visit.

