10.5. Analysis of Primary Endpoint

The primary endpoint of the study is the proportion of subjects achieving post-operative mechanical alignment, defined as $\pm 3^\circ$ from target, assessed at the 1 month study visit, and after undergoing a Navio assisted TKA.

The proportion defined above will be presented along with the associated two-sided 95% confidence interval, to be calculated using exact binomial methods.

Superiority of the proportion of subjects achieving post-operative mechanical alignment, after undergoing a Navio assisted TKA against those in the reference literature (Parratte et al.)⁷ will be achieved if the lower limit of the two-sided 95% confidence interval is greater than 73.4%.

Mechanical alignment will also be summarized using summary statistics.

10.6. Analysis of Secondary Endpoints:

Implant survival rate will be assessed for a final analysis using the number and proportion of subjects who had no implant revisions by the 2-year time point, the associated 95% confidence intervals will be calculated using exact binomial methods. Time to occurrence of revisions will also be analyzed using Kaplan-Meier survival analysis.

KSS, EQ-5D-5L, and FJS scores will be analyzed separately at the end of study using Repeated Measures ANOVA models, prognostic and baseline factors will be adjusted for.

Length of hospital stay, operative time (both skin to skin time and anesthetic time), and radiographic assessments will be assessed using summary statistics. Trends in operative time measures for individual investigators over the course of the study will be assessed.

10.7. Analysis of Safety Endpoints:

The safety endpoints for this study are the number of occurrences and the frequency of subjects reporting: adverse events (AE), serious adverse events (SAE), adverse device effects (ADE), serious adverse device effects (SADE), unanticipated serious adverse device effects (USADE) and device deficiencies (DevD).

In addition, for each event, the following will be summarised: seriousness, the relationship to the investigational device (Navio), relationship to implant, relationship to study procedure, outcome and either the duration of the resolved events or the duration of the events at study completion.

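### The 80% power stated for 115 subjects does not come from the planned exact one-sample test, which has about 97–98% power at a true rate of 88%

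*Combined protocol and SAP*

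**What the plan says.** The synopsis describes a "Multicenter, prospective single-arm cohort study with historical control". Section 10.1 takes its reference rate from a published series of 398 knees, in which "there were 292 (73.4%) which post-operatively were defined as mechanically aligned". It assumes that "the proportion of mechanically aligned TKAs using the Navio system will be around 88" per cent. On that basis it states that "the recruitment of 115 subjects would be sufficient to provide 80% power to show that the lower limit" of the two-sided 95% confidence interval is above 73.4%. It then raises 115 to 120 for about 5% loss by the one-month visit.

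Section 10.5 gives the matching analysis. The interval is "to be calculated using exact binomial methods", and superiority is achieved "if the lower limit of the two-sided 95% confidence interval is greater than 73.4" per cent. Sections 10.1 and 10.5 therefore state the same decision rule, with 73.4% as a fixed number. No formula, software or variance for the historical series is given for the 80%.

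Section 4 gives the sample a further purpose, "to collect 2-year safety and effectiveness data on 120 subjects", which section 10.1 does not mention.

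**The concern.** Every input to the power calculation is stated, so the 80% should be reproducible, and it is not. A difference of 14.6 percentage points (88 − 73.4) tested in one arm against a fixed value does not need 115 subjects for 80% power.

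What is at stake is the description of the design. A reader of section 10.1 takes the type II error at 88% to be 20%, when it is about 2–3%. The reader also has no way to see that a true rate well below 88% would probably be declared superior. Anyone who checks the figure will ask whether a different comparison was intended.

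**Working it through.** **Inputs**

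- Reference rate p0 = 0.734, fixed (10.1, 10.5)
- Assumed true rate p1 = 0.88 (10.1)
- Success if the lower limit of the two-sided 95% interval exceeds p0, so 2.5% in the relevant tail (10.1, 10.5)
- Exact binomial interval (10.5), taken as Clopper-Pearson
- n = 115 (10.1); n = 120 recruited; n = 114 evaluable after 5% loss (120 × 0.95)

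**Step 1: the plan's own figure.** The rule succeeds when the number aligned, x, reaches the smallest value for which the 2.5% quantile of Beta(x, n − x + 1) exceeds 0.734. Power is P(X ≥ x) with X ~ Binomial(n, 0.88). For n = 115, x = 94 gives a lower limit of 0.7345 and x = 93 falls short, so the cut-off is 94. Then P(X ≥ 94 | 0.88) = 0.982, against 0.80 stated.

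**Step 2: the neighbouring sample sizes**

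| n | Cut-off | Observed rate at cut-off | Lower limit | Power at 88% | Power at 85% | One-sided type I error | True rate for 80% power |
|---|---|---|---|---|---|---|---|
| 114 | 94 | 82.5% | 0.742 | 97.0% | 81.6% | 1.6% | 84.8% |
| 115 | 94 | 81.7% | 0.7345 | 98.2% | 86.5% | 2.4% | 84.1% |
| 120 | 98 | 81.7% | 0.736 | 98.5% | 87.4% | 2.3% | 84.0% |

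**Step 3: the n that gives 80%.** In a search from n = 20 to 300, exact power at 88% first reaches 80% at n = 60 (82.2%). Because the binomial is discrete it dips below again, for the last time at n = 69 (79.9%), and stays above 80% from n = 70 (87.1%). The one-sample normal approximation agrees:

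n = [(1.960·√(0.734 × 0.266) + 0.842·√(0.88 × 0.12)) / 0.146]² = [(0.866 + 0.273) / 0.146]² ≈ 60.9.

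So 115 is about 1.6 to 1.9 times what 80% power requires (115/70 and 115/60).

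**Step 4: could another interval explain it?** At n = 115 a Wilson interval has the same cut-off of 94 and 98.2% power. A Wald interval has cut-off 93 and 99.1% power. Even a 99% exact interval (cut-off 97) has 90.7%. No one-sample method tried at the stated level and threshold gives about 80%.

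**Step 5: could another comparison explain it?** The usual formula for two parallel groups of equal size, 73.4% against 88%, with mean rate 0.807, gives

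n = [(1.960·√(2 × 0.807 × 0.193) + 0.842·√(0.734 × 0.266 + 0.88 × 0.12)) / 0.146]² ≈ 113.5 per group,

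or 110.8 with unpooled variance. That is close to 115, but it belongs to a design this trial does not have, and the documents do not say it was used. If the 292/398 were treated as a sample with its own error (Newcombe interval for the difference, control count varying), power at 88% would be 93.8%, 94.1% and 94.6% at n = 114, 115 and 120, which is not 80% either.

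**The case against.** The strongest reply is that the sentence is not false. A design with 98% power is sufficient for 80%, sections 10.1 and 10.5 state the same rule, and 88% is offered as an expected rate rather than the smallest detectable one. No estimate, interval or conclusion would change. Section 4 gives 120 subjects a second purpose, and section 11.4 describes surgery and follow-up as the same as outside the study, so the extra subjects are not an obvious burden.

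Most of that stands as a limit on the importance of the point. It does not rescue the figure. The section exists to show why N has the value it has, and 80% is true there only as a loose lower bound.

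A second reply is that 97–98% presumes subjects without a one-month film leave the denominator. Section 10.3 defers missing-data rules to a SAP still to be written, and the mITT set in 10.4 requires only one post-baseline assessment. If six of 120 were missing and counted as failures, 98 successes would be needed from 114 observed knees, and power at 88% would be 79.6%. The plan states no such rule, and raising 115 to 120 for loss implies that lost subjects are excluded, so this is not the source of the 80%. It is a good reason to tie the restated power to evaluable subjects.

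**Conclusion.** The concern holds. The stated 80% is not a property of the planned test: at a true rate of 88% the exact one-sample rule has 97.0% to 98.5% power for 114 to 120 evaluable subjects. With those numbers 80% power is reached at a true rate of about 84–85%, roughly 11 points above the reference rather than 14.6.

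The error is conservative. The trial is not underpowered, the attained one-sided type I error is 1.6% to 2.4%, and the threshold and success rule are unaffected. It should be fixed because the justification of N is wrong as written and cannot be reproduced.

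The result assumes a Clopper-Pearson interval, 73.4% as a fixed reference, and subjects without a one-month alignment result excluded from the denominator. The first assumption hardly matters, as the Wilson and Wald results show. The two-group formula as the origin of 115 remains a conjecture.

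**What to change.** Keep 120 subjects and the rule in 10.5, and restate 10.1 along these lines:

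> With 114 to 120 evaluable subjects, the exact one-sample test in section 10.5 has about 97–98% power if the true proportion aligned is 88%, and 80% power if it is about 84–85%. For illustration, success requires at least 94 of 114, 94 of 115 or 98 of 120 subjects aligned.

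Define evaluable there as having a one-month alignment result. If the number was also chosen to support the two-year safety and effectiveness data in section 4, say so in 10.1 as part of the justification. If a comparison allowing for sampling error in the 292/398 was intended, 10.5 would have to state it, and its power at 88% (about 94%) would replace the 80%.

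The cost is a rewording of 10.1. Enrolment, the success rule and the analysis do not change.

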10.2. General Statistical Considerations

Smith & Nephew's Global Biostatistics group will conduct the statistical analysis for this study and they will prepare Statistical Analysis Plan (SAP). Unless otherwise stated, all significance tests and hypothesis testing will be two-sided, performed at the 5% significance level. Resulting p-values will be quoted and 95% two-sided confidence intervals will be generated where appropriate. All p-values will be rounded to three decimal places, p-values less than 0.001 will be presented as ' <0.001 ' in all tables.

Where data summaries are specified, categorical and ordinal variables will be summarized with frequencies and percentages. Continuous variables will be summarized with the following summary statistics: number of observations, mean, median, standard deviation, minimum and maximum values. All analyses will be performed in SAS 9.4 (or later).

10.3. Missing Data

A complete disposition report, along with the explanation for lost-to-follow-up, death, revision, and withdrawn subjects is to be provided in the Clinical Study Report (CSR). The methods used to handle missing or incomplete data for the efficacy and safety measures will be detailed in the Statistical Analysis Plan (SAP).

10.4. Analysis Populations

All subjects that are operated on by the study device are considered study participants. The following study populations and analysis sets will be defined:

- **Safety Population:** This population will include all subjects that received the study device and will be used for analysis of demographics, disposition data and safety.
- **Modified Intention to Treat Population (mITT):** Following the intention to treat principle, this population Full Analysis Set (FAS): This will include all subjects that received the study device and attended at least one post-baseline assessment. This population will be used for the primary analysis of all efficacy endpoints.
- **Per Protocol Population (PP):** This population will include all subjects that received the study device, meet the inclusion/exclusion criteria, attend all follow-up assessments within the specified window, and have no significant protocol deviations. Subjects that are required to be withdrawn from the study under the protocol (e.g. due to revision) will be included regardless of attendance of follow-up visits unless they are deemed to have significant protocol deviations or failed to meet the inclusion/exclusion criteria. This population will be used as secondary analysis of all efficacy endpoints.

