8.3. Conditions for Study Termination

All reasonable efforts should be made to retain the subjects for the 2 year duration of this study. If the subject has a revision of any component, the subject will be terminated from the study.

A. Screening Failure

If a subject has provided consent, completed screening and for any reason is not operated on by the study device and does not receive a total knee implant from the Journey II BCS or Cruciate-Retraining (CR) Systems, the subject will not be considered enrolled in the study.

For these subjects an Inclusion/Exclusion and Informed Consent CRF, Demographics CRF, Medical History CRF, and End of Study CRF need to be completed. However, the CRFs should not be submitted into the Sponsor's database unless the subject signed consent and was assigned a Subject ID.

B. Voluntary Withdrawal

Study participation is voluntary and subjects may withdraw at any point during the study without giving their reason for doing so. An End of Study CRF will be completed for all subjects who do not finish the study, and reason for withdrawal will be documented in the form.

C. Lost to Follow-Up

Some actively enrolled subjects may not return for follow-up exams due to a variety of reasons. Study personnel must make reasonable efforts to contact the subject and document the following contact attempts prior to declaring a subject to be lost to follow-up: the subject has been contacted according to the site's policies, but no less than 2 documented phone contacts and 1 certified letter without response. Copies of all attempts to reach the subjects per regular mail or email and/or the attempts to contact the subject via other means should be documented and that documentation should be kept with the subjects CRF at the site. A subject will be considered lost to follow-up if he/she does not appear for the scheduled study visit for 2 consecutive visits and study personnel are unable to contact the subject.

D. Study Termination by Investigator/Sponsor

The Investigator **may** withdraw subjects from the study for many reasons, including but not limited to the following:

- subject noncompliance to study schematic
- subject lost to follow-up

The Investigator **should** withdraw subjects from the study:

- in case any component of the original Journey II hardware is revised/exchanged
- if the Investigator or the Sponsor stops the study for any reason

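### The per-protocol analysis of 1-month alignment drops subjects for missed or out-of-window visits at 6, 12 or 24 months, when alignment is not measured

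*Combined protocol and SAP*

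**What the plan says.** Section 10.4 of the protocol sets out one PP population. Besides receiving the study device and meeting the eligibility criteria, subjects must "attend all follow-up assessments within the specified window, and have no significant protocol deviations". There is one exemption: subjects "required to be withdrawn from the study under the protocol (e.g. due to revision) will be included regardless of attendance", provided they met the entry criteria and had no significant deviation. On use, the section says: "This population will be used as secondary analysis of all efficacy endpoints". For the mITT/FAS set it says: "This population will be used for the primary analysis of all efficacy endpoints".

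The primary endpoint (sections 3.1 and 10.5) is alignment at the 1-month visit. Sections 7.2 and 7.4 place long-leg films at the pre-operative and 1-month visits. Section 7.5 lists only standard AP, lateral and patellar films at 6 months, 1 year and 2 years. The windows in section 7.1 are 30±7, 182±30, 365±60 and 730±60 days.

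Section 8.3 separates two kinds of investigator withdrawal. The investigator *should* withdraw a subject "in case any component of the original Journey II hardware is revised/exchanged", or if the study is stopped. The investigator *may* withdraw a subject for "subject noncompliance to study schematic" or for loss to follow-up, and a subject counts as lost if he or she "does not appear for the scheduled study visit for 2 consecutive visits" and cannot be contacted. Separately, "subjects may withdraw at any point during the study without giving their reason for doing so".

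**The concern.** A PP analysis of alignment is useful if it shows whether departures from protocol that bear on alignment change the result. Under this definition, membership also depends on attendance during the two years after surgery, at visits that add nothing to the alignment outcome. A difference between the mITT and PP alignment results could then reflect who kept returning, and the reader could not separate that from the effect of relevant deviations. Usable films are also set aside, which widens the interval for no gain.

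Operative time and length of stay are filtered in the same way although both are known by discharge. That matters less, because section 10.6 only summarises them.

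**Working it through.** **Step 1: which visits supply alignment data.**

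| Visit | Window (days) | Long-leg film | Needed for PP |
|---|---|---|---|
| 1 month | 30±7 | yes | yes |
| 6 months | 182±30 | no | yes |
| 1 year | 365±60 | no | yes |
| 2 years | 730±60 | no | yes |

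Three of the four attendance conditions have no bearing on the alignment measurement.

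**Step 2: whom the exemption covers.** Section 10.4 exempts required withdrawals and gives revision as its example. Section 8.3 says the investigator *should* withdraw for revision or exchange and for a stopped study. Schedule noncompliance and loss to follow-up fall under *may*, and voluntary withdrawal is the subject's own decision. Read together, ordinary non-attenders are not exempt.

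**Step 3: how many films are lost.** The plan gives no expected PP size. Its only attendance figure is about 5% loss at 1 month (section 10.1), which gives 120 × 0.95 = 114 films. That is an upper figure for in-window films, because the 5% covers loss and not lateness.

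Let q be the proportion attending each later visit in window. The documents do not give q; 0.85 to 0.95 is assumed. There are two bounding patterns:

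- the same subjects miss every later visit: share dropped = 1 − q, PP n = 114q;
- attendance is independent across the three visits: share dropped = 1 − q³, PP n = 114q³.

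The half-width is half the exact (Clopper-Pearson) 95% interval at x = round(0.88n), where 88% is the plan's expected proportion. With all 114 films (100/114) it is 6.4 points.

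| q | Same subjects: dropped | PP n | Half-width (points) | Independent: dropped | PP n | Half-width (points) |
|---|---|---|---|---|---|---|
| 0.95 | 5% | 108 | 6.6 | 14.3% | 98 | 7.0 |
| 0.92 | 8% | 105 | 6.7 | 22.1% | 89 | 7.4 |
| 0.90 | 10% | 103 | 6.7 | 27.1% | 83 | 7.6 |
| 0.85 | 15% | 97 | 7.0 | 38.6% | 70 | 8.1 |

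Example: at q = 0.90 under independence, 0.90³ = 0.729, so 27.1% are dropped and 114 × 0.729 = 83 remain.

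**Step 4: sensitivity to the start.** If only 90% have an in-window 1-month film, the start is 120 × 0.90 = 108 films, with a half-width of 6.6 points. PP then keeps 92–103 subjects (half-width 6.7–7.1 points) if the same subjects miss, or 66–93 (7.1–8.6 points) under independence.

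**Step 5: where in the range.** Section 8.3 defines loss through consecutive missed visits, and a subject who withdraws misses every visit afterwards. Misses will therefore cluster, and for a given q the loss should fall below the independent figure. The wide later windows make q = 0.85 look pessimistic. PP has no power target, so no power claim is made.

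**The case against.** The strongest reply is that little depends on this. PP is secondary, and the superiority decision rests on the mITT set. In the least favourable case from 114 films (62/70 aligned), the exact interval runs from 78.7% to 94.9%, still above the 73.4% reference. If misses fall on the same subjects, the half-width grows by only 0.2 to 0.6 points. Every rate behind the larger figures is assumed. All of this stands and sets the weight of the point.

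A second reply is that one PP set for full adherence is a recognised choice. It keeps the same subjects across endpoints, suits the scores followed to 2 years, and agrees with section 13, which counts out-of-window visits as deviations. That has some force for the Knee Society Score, EQ-5D-5L and Forgotten Joint Score, but little for one radiograph taken at 1 month. Section 13 does not make every late visit a significant deviation, though any new wording should refer to it.

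Third, the exemption is open-ended: revision is only an example, and section 8.3 never uses the word required. That non-attenders fall outside it is an inference from *should* and *may*. It is the natural reading, but it is not spelled out.

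Finally, a fuller SAP might define PP by endpoint. Section 10.3 defers only missing-data methods to it, and nothing in the supplied text narrows the rule in section 10.4.

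**Conclusion.** The concern holds. Applied as written, section 10.4 removes valid 1-month alignment results from the PP analysis because of later events that carry no alignment information. Confidence in this reading of the definition is high.

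Its size is uncertain and probably modest: 5–15% of films if the same subjects miss every later visit, with 14–39% under independence as an upper comparison, all resting on assumed in-window attendance of 85–95%. Any selection bias is of unknown size and direction. The exemption for revision, the withdrawal most plausibly linked to a poor knee result, reduces that worry. The primary mITT analysis and the section 10.5 success rule are not affected. The change is optional but worth making because it is cheap and makes the mITT–PP comparison easier to interpret.

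**What to change.** Before any analysis, define PP membership by endpoint in section 10.4 or the SAP:

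- **Alignment:** study device received; inclusion and exclusion criteria met; 1-month long-leg film within 30±7 days; no significant deviation affecting alignment. State that a missed or out-of-window 6-, 12- or 24-month visit is not such a deviation, and cross-refer to section 13 so that it does not re-enter as one.
- **Endpoints measured at later visits:** apply attendance at those visits to these endpoints only.
- **Operative time and length of stay:** no follow-up attendance condition.
- **Required withdrawals:** keep the present exemption.

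The cost is one paragraph and one extra analysis flag, with no new data. The drawback is that PP denominators will differ by endpoint, so the plan gives up a single common set of PP subjects. Settle it before results are seen, since a later redefinition could look selective.
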